10.2 Serious Adverse Events

A serious adverse event (SAE) is any untoward medical occurrence that at any dose meets 1 or more of the following criteria:

- Is fatal
- Is life threatening
- Note: Life-threatening refers to an event that places the subject at immediate risk of death. This definition does not include a reaction that, had it occurred in a more severe form, might have caused death.
- Requires or prolongs inpatient hospitalization.
- Results in persistent or significant disability or incapacity
- Is a congenital anomaly or birth defect in the child or fetus of a subject exposed to IP prior to conception or during pregnancy
- Is an important medical event or reaction that, based on medical judgment, may jeopardize the subject or require intervention to prevent one of the above consequences (eg, anaphylaxis)

All adverse events that do not meet any of the criteria for SAEs should be regarded as non-serious AEs.

10.2.1 Events of Special Interest (EOSI)

The following EOSI need to be reported to the Sponsor within 24 hours of site awareness, irrespective of seriousness, severity or causality:

- Elevation of $ALT \ge 1.5x$ ULN, regardless of whether that triggers an initiation or modification of corticosteroid treatment
- Thromboembolic event

10.3 Methods and Timing for Capturing and Assessing Safety Parameters

10.3.1 Adverse Event Reporting Period

The study AE reporting period is as follows: After informed consent but prior to initiation of study treatment, only SAEs associated with any protocol-imposed interventions will be reported. After informed consent is obtained and the first administration of study drug, the reporting period for all non-serious AEs and SAEs begins and continues for approximately 5 years or until study discontinuation/termination, whichever is longer. The criteria for determining, and the reporting of SAEs is provided in Section 10.1.1.1.

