10.4.1.8 Deaths

All deaths that occur during the AE reporting period (refer to Section 10.3.1), regardless of attribution, will be recorded on the AE eCRF and expeditiously reported to the Sponsor as an SAE.

When recording a death, the event or condition that caused or contributed to the fatal outcome should be recorded as the single medical concept on the eCRF. If the cause of death is unknown and cannot be ascertained at the time of reporting, record "Unexplained Death" or "Death of Unknown Cause" on the AE eCRF.

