10.4.1.9 Pregnancy

Although not an AE per se, pregnancy in the partner of a subject taking trial medication should be reported expeditiously to the Sponsor to facilitate outcome monitoring by the Sponsor. Pregnancy in partner should be reported during the period up to 5 years after viral infusion.

Pregnancy in a partner should be reported within 24 hours of the site becoming aware of the pregnancy by entering the information on the Pregnancy eCRF and submitting to BPV within 24 hours of the site becoming aware of the event. The Investigator must make every effort to follow the subject's partner (with that partner's consent) through resolution of the pregnancy (delivery or termination) and to report the resolution on the Pregnancy Follow-up eCRF. In the event of pregnancy in the partner of a study subject, the Investigator should make every reasonable attempt to obtain the woman's consent for release of protected health information.

Abortion, whether therapeutic or spontaneous, should always be classified as an SAE (as the Sponsor considers these to be medically significant), recorded on the AE eCRF, and expeditiously reported to the Sponsor as an SAE.

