10.5 Reporting Requirements

10.5.1 Expedited Reporting Requirements

All SAEs and EOSI that occur during the course of the AE Reporting Period (refer to Section 10.3.1), whether or not considered related to study drug, must be reported by entering the information in the AE eCRF and submitting to BPV within 24 hours of the site becoming aware of the event. Investigators should not wait to collect information that fully documents the event before notifying BPV of an SAE. BioMarin may be required to report certain SAEs to regulatory authorities within 7 calendar days of being notified about the event; therefore, it is important that Investigators submit any information requested by BioMarin as soon as it becomes available.

The Sponsor is responsible for identifying, preparing and reporting all SUSARs to the relevant competent authorities, ethics committees and investigators in accordance with the requirements identified in the Clinical Trials Regulations.

If the EDC is unavailable, all SAEs should be reported to BPV by completing the SAE Report Form and faxing or emailing the completed form to BPV within 24 hours of the site becoming aware of the event. Once the EDC is available, the information should be entered in the AE eCRF.

270-201 Amendment 8

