10.7 Post-Study Adverse Events

At the last scheduled visit, the Investigator should instruct each subject to report, to the Investigator and/or to BPV directly, any subsequent SAEs that the subject's personal physician(s) believes might be related to prior study treatment.

The Investigator should notify the study Sponsor of any death or SAE occurring at any time after a subject has discontinued or terminated study participation, if the Investigator believes that the death or SAE may have been related to prior study treatment. The Sponsor should also be notified if the Investigator should become aware of the development of cancer or of a congenital anomaly in a subsequently conceived offspring of a subject that participated in this study.

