12.10 Early Termination Visit

The Early Termination visit will occur on the date the subject withdraws from the study, even if the date does not correspond to a protocol-specific visit.

If a subject leaves the study prior to the Week 260 visit, the subject will be asked to return to the study site and complete an Early Termination visit. At the Early Termination visit, as many of the following assessments as possible should be done:

- Physical examination
- Assessment of Adverse Events and Concomitant Medications (including review of subject diary for bleeding and FVIII use)
- Vital Signs
- Blood chemistry, haematology, coagulation screen, and CRP (refer to Table 9.7.8.2.1)
- Urine Tests (refer to Table 9.7.8.2.1)
- Liver Tests (refer to Table 9.7.8.3.1) local laboratory assessment
- FVIII activity level local laboratory assessment
 - FVIII activity level (one-stage clotting assay)

- FVIII activity level (chromogenic substrate assay)
- Liver Tests (refer to Table 9.7.8.3.1) central laboratory assessment
- FVIII Assays central laboratory assessment
 - FVIII activity level (one-stage clotting assay)
 - FVIII activity level (chromogenic substrate assay)
 - FVIII coagulation activity exploratory assay
 - o Bethesda assay (with Nijmegen modification) for FVIII inhibitor level
 - FVIII antigen (ELISA)

Note: If a subject has used FVIII within 72 hours of a measurement day, all efforts should be made to obtain FVIII activity measurements when a 72-hour interval without FVIII use is achieved; the 72-hour wash-out period is only intended for subjects who have achieved FVIII \geq 5 IU/dL at 16 weeks after BMN 270 infusion and who have not resumed standard of care FVIII replacement therapy.

- AAV5 antibody titer
- FVIII antibody titer
- PBMC collection
- VWF:Ag
- PCR of vector DNA in blood, saliva, urine, semen, and stools
 - Sample testing at the ETV is not required if at least 3 consecutive samples are clear during the Post-Infusion Follow-Up period.
- Exploratory biomarker assessment
- Haemo-QoL-A QOL assessment

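### For dosed subjects who leave before 5 years, Sections 10.3.1 and 10.7 set different reporting rules for the same weeks, and following 10.7 filters deaths and SAEs by causality opinion

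*Protocol*

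**What the plan says.** Section 10.3.1 states that, once study drug has been given, "the reporting period for all non-serious AEs and SAEs begins" and "continues for approximately 5 years or until study discontinuation/termination, whichever is longer". Two other sections depend on that period. Section 10.4.1.8: "All deaths that occur during the AE reporting period (refer to Section 10.3.1), regardless of attribution, will be recorded on the AE eCRF". Section 10.5.1 adds that SAEs and EOSI in the same period, "whether or not considered related to study drug, must be reported by entering the information in the AE eCRF".

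Section 10.7 governs any time after a subject's participation has been discontinued or terminated. It asks the investigator to notify the sponsor of a death or SAE "if the Investigator believes that the death or SAE may have been related to prior study treatment". Cancer, and a congenital anomaly in a child conceived later, are to be notified if the investigator becomes aware of them, with no causality condition. Non-serious AEs and EOSI are not mentioned.

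Two further provisions matter. Section 12.10: "The Early Termination visit will occur on the date the subject withdraws from the study"; no later contact is scheduled for such a subject. Section 10.4.1.9: "Pregnancy in partner should be reported during the period up to 5 years after viral infusion".

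**The concern.** Safety is the first primary objective (Section 8), and Section 9.1 evaluates it for about 5 years after dosing. Exposure comes from one infusion designed to give lasting expression (Section 7.3), so leaving the study does not end it. There is no control group (Section 9.2), at most 15 subjects are dosed (Section 14.7), and those who withdraw are not replaced (Section 9.3.5).

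In this setting a subject who leaves early is covered by a broad rule and a narrow rule at once. Under the broad rule, a death judged unrelated two years after exit is an expedited report. Under the narrow rule it need not be reported. If sites differ in the section they follow, or all follow the narrower one, late deaths and SAEs of early leavers enter the safety record according to an opinion about cause. That opinion is hard to form for late events in a first-in-human gene therapy with no comparator.

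**Working it through.** **Horizon.** Section 9.3.6 gives about 264 weeks per subject: 4 weeks of screening, 1 day of infusion, 16 weeks and 244 weeks of follow-up. Check: 4 + 1/7 + 16 + 244 = 264.14, which reproduces the stated figure. After infusion: 16 + 244 = 260 weeks, and 260 × 7 / 365.25 = 4.98 years, consistent with about 5 years.

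**End of the 10.3.1 period.** For a subject leaving at Week w, the longer of the two limits is at least max(260, w) = 260 weeks. This holds whether the discontinuation or termination in 10.3.1 means the subject's or the study's; the second meaning could only lengthen the period.

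**The two rules from exit to Week 260:**

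| Event | 10.3.1 with 10.4.1.8 and 10.5.1 | 10.7 |
|---|---|---|
| Death | Report, any cause | Only if the investigator believes it may be related |
| SAE other than cancer or offspring anomaly | Report, any cause | Only if the investigator believes it may be related |
| Cancer | No causality condition | No causality condition, if the investigator becomes aware |
| Congenital anomaly in later offspring | No causality condition (an SAE criterion in 10.2) | No causality condition, if the investigator becomes aware |
| EOSI, not serious | Report, any cause | Not mentioned |
| Non-serious AE | Report | Not mentioned |

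Partner pregnancy is outside both columns: 10.4.1.9 asks for it to 5 years.

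**Length of the overlap**, 260 − w. The exit weeks are assumptions, since the protocol gives no dropout rate:

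| Exit at Week | Weeks under both rules | Share of 260 |
|---|---|---|
| 16 | 244 | 94% |
| 52 | 208 | 80% |
| 104 | 156 | 60% |
| 156 | 104 | 40% |

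For the whole study with 15 dosed, planned follow-up is 15 × 260 = 3,900 subject-weeks. One exit at Week 52 puts 208 / 3,900 = 5.3% of it under both rules.

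**Means of collection.** Section 10.3.2 elicits AEs at subject contacts. After the Early Termination visit none is planned, so the broad duty has no scheduled route, although the pregnancy rule assumes that some information still arrives.

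**The case against.** The strongest reply is that the two sections can coexist. Section 10.7 is headed as post-study, opens with the last scheduled visit, and sets a minimum. It does not forbid reporting other events, so a site that reports everything it learns of under 10.3.1 also meets 10.7. That stands. A reader might infer that a site cannot comply with both sections, and the text does not support this: the duties differ in breadth without excluding each other.

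A reader might also infer that nothing but events believed related is captured after exit. That is wrong too. Cancer and offspring anomaly carry no causality condition, partner pregnancy is reportable to 5 years, and Section 10.6 keeps following unresolved AEs and SAEs. The condition itself is mild: a possible relationship suffices, and Section 10.3.3.3 defines related broadly.

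The group concerned may be small. Treatment failures may move to the abbreviated schedule in Section 12.8, where AEs are still assessed, and Section 9.3.4 ends all collection once data permission is withdrawn.

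What the reply does not remove is the missing precedence. The investigator's duty in 10.7 runs from the end of the subject's participation and is not limited to those who complete 5 years. Section 10.8 shows that the protocol can end a period at the Early Termination visit when it means to; 10.3.1 does not. Nor is withdrawal always refusal of contact, because Section 9.3.4 lets the investigator or sponsor remove a subject, for example for non-adherence.

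**Conclusion.** The inconsistency is real and should be corrected. For a dosed subject who leaves before about 5 years, the broad and narrow rules cover the same weeks, no order of precedence is given, and no contact is planned through which the broad rule could be met. A site that follows 10.7 alone complies with its wording and still filters deaths, and SAEs other than cancer and offspring anomaly, by causality opinion inside the primary safety window. It also reports no non-serious EOSI.

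The size per subject is 260 minus the exit week: 104 to 244 weeks for exits between Week 156 and Week 16. How many subjects this touches cannot be derived from the protocol. A reader might go on to infer that the 5-year safety record is lost or the event rates biased by a known amount. The protocol does not support this: it gives no dropout rate, nothing shows that an event would be missed, and the handling of leavers in the safety tables may properly be left to the SAP.

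**What to change.** Reconcile 10.3.1 and 10.7 with one end rule for dosed subjects who leave early and have neither refused contact nor withdrawn data permission:

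- Until 5 years after infusion, deaths, SAEs and thromboembolic events that the site learns of are reported regardless of causality, alongside the cancer, congenital anomaly and partner pregnancy reporting already required.
- Collection of non-serious AEs ends at the Early Termination visit.
- The causality condition in 10.7 applies only after the 5-year period or after refusal of contact.

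Sections 10.4.1.8 and 10.5.1 then need only refer to the revised period.

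Optionally, add a brief vital-status call or record check at each End of Year date, so that the rule has a means of collection. This is a design choice; the inconsistency can be cured without it.

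The cost is an amendment to two sections with matching consent wording. If the optional check is adopted, it adds at most one call or record check per remaining End of Year date for each early leaver, in a study of up to 15 subjects.

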10.3.2 Eliciting Adverse Events

Investigators will seek information on AEs, SAEs, and EOSI at each subject contact by specific questioning and, as appropriate, by examination. Information on all AEs and SAEs and EOSI, should be recorded in the subject's medical record and on the AE Case Report Form (eCRF).

10.3.3 Assessment of Seriousness, Severity, and Causality

The Investigator responsible for the care of the subject or medically qualified designee will assess AEs for severity, relationship to study drug, and seriousness (refer to Section 10.1.1.1 for SAE definitions). These assessments must be made by a study clinician with the training and authority to make a diagnosis (eg, MD/DO, physician's assistant, nurse practitioner, or DDS).

10.3.3.1 Seriousness

The investigator will assess if an AE should be classified as "serious" based on the seriousness criteria enumerated in Section 10.1.1.1. Seriousness serves as a guide for defining regulatory reporting obligations.

10.3.3.2 Severity

Severity (as in mild, moderate, or severe headache) is not equivalent to seriousness, which is based on subject/event outcome or action criteria usually associated with events that pose a threat to a subject's life or functioning. The severity of each will be assessed using the defined categories in Table 10.3.3.2.1.

The Investigator will determine the severity of each AE and SAE and EOSI using the NCI CTCAE v4. Adverse events that do not have a corresponding CTCAE term will be assessed according to the general guidelines for grading used in the CTCAE v4 as stated below.

Table 10.3.3.2.1: Adverse Event Grading (Severity) Scale

Grade	Description	
1	Mild: asymptomatic or mild symptoms; clinical or diagnostic observat indicated	ions only; intervention not
2	Moderate: minimal, local or noninvasive intervention indicated; limiting age-appropriate instrumental activities of daily living (ADL) ^a	
3	Severe or medically significant but not immediately life-threatening: hospitalization or prolongation of hospitalization indicated; disabling; limiting self-care ADL ^b	
4	Life threatening or debilitating: consequences; urgent intervention indicated	Grade 4 and 5 AEs should always be
5	Death related to AE	reported as SAEs

^a Instrumental ADL refer to the following examples: preparing meals, shopping for groceries or clothes, using the telephone, managing money.

^b Self-care ADL refer to the following examples: bathing, dressing and undressing, feeding oneself, using the toilet, taking medications, not bedridden.

10.3.3.3 Causality

The Investigator will determine the relationship of an AE to the study drug and will record it on the source documents and AE CRF. To ensure consistency of causality assessments, Investigators should apply the guidance in Table 10.3.3.3.1.

Table 10.3.3.3.1: Causality Attribution Guidance

Relationship	Description	
Not Related	Exposure to the IP has not occurred	
	• OR	
	• The administration of the IP and the occurrence of the AE are not reasonably related in time	
	• OR	
	• The AE is considered likely to be related to an etiology other than the use of the IP; that is, there are no facts, evidence, or arguments to suggest a causal relationship to the IP.	
Related	• The administration of the IP and the occurrence of the AE are reasonably related in time	
	AND	
	• The AE could possibly be explained by factors or causes other than exposure to the IP	
	OR	
	• The administration of IP and the occurrence of the AE are reasonably related in time	
	AND	
	• The AE is more likely explained by exposure to the IP than by other factors or causes.	

Factors suggestive of a causal relationship could include (but are not limited to):

- Plausible temporal relationship
- Absence of alternative explanations
- Rarity of event in a given patient or disease state
- Absence of event prior to study drug exposure
- Consistency with study product pharmacology
- Known relationship to underlying mechanism of study drug action
- Similarity to adverse reactions seen with related drug products
- Abatement of AE with discontinuation of study drug, and/or recurrence of AE with reintroduction of study drug

The investigator's assessment of causality for individual AE reports is part of the study documentation process. Regardless of the Investigator's assessment of causality for individual AE reports, the Sponsor will promptly evaluate all reported SAEs against cumulative product experience to identify and expeditiously communicate possible new safety findings to investigators and applicable regulatory authorities.

10.4 Procedures for Recording Adverse Events

10.4.1 Recording Adverse Events on a eCRF

Investigators should use precise medical terminology when recording AEs or SAEs on the AE eCRF. Avoid colloquialisms and abbreviations.

Record only one diagnosis, sign, or symptom per event field on the AE eCRF (eg, nausea and vomiting should not be recorded in the same entry, but as 2 separate entries).

In order to classify AEs and diseases, preferred terms will be assigned by the Sponsor to the original terms entered on the AE eCRF, using MedDRA (Medical Dictionary for Regulatory Activities) terminology.

10.4.1.1 Diagnosis versus Signs and Symptoms

Using accepted medical terminology, enter the diagnosis (if known). If not known, enter sign(s) and/or symptom(s). If a diagnosis subsequently becomes available, then this diagnosis should be entered on the AE (or SAE, as appropriate) eCRF, replacing the original entries where appropriate.

10.4.1.2 Adverse Events Occurring Secondary to Other Events

In general, AEs occurring secondary to other events (eg, cascade events) should be identified by their primary cause. For example, if severe diarrhea is known to have resulted in dehydration, it is sufficient to record only diarrhea as an AE or SAE on the AE eCRF. However, medically important events that may be linked and/or separated in time should be recorded as independent events on the AE eCRF. For example, if severe haemorrhage leads to renal failure, both events should be recorded separately on the AE eCRF.

10.4.1.3 Persistent or Recurrent Adverse Events

A persistent AE (duration of adverse event > 7 days) is one that extends continuously, without resolution, between subject evaluation time points. Events that change in severity necessitate the recording of an additional AE. AEs that do not have a change in severity should be recorded only once on the eCRF.

A recurrent AE is one that occurs and resolves between subject evaluation time points, but then subsequently recurs. All recurrences of the AE should be recorded on the AE eCRF.

10.4.1.4 Abnormal Laboratory Values

Laboratory test results will be recorded on the laboratory results pages of the AE eCRF, or appear on electronically produced laboratory reports submitted directly from the central laboratory, if applicable.

Any laboratory result abnormality fulfilling the criteria for a SAE or EOSI should be reported as such, and recorded in the AE eCRF. Any laboratory result abnormality of CTCAE Grade 4 or 5 should be recorded as an SAE in the AE eCRF.

A clinical laboratory abnormality is considered clinically significant and should be documented as an AE if not refuted by a repeat test to confirm the abnormality and **any** one or more of the following conditions is met:

- Accompanied by clinical symptoms
- Requiring a change in concomitant therapy (eg, addition of, interruption of, discontinuation of, or any other change in a concomitant medication, therapy or treatment).
- The abnormality suggests a disease and/or organ toxicity
- The abnormality is of a degree that requires active management (eg, change of dose, discontinuation of study drug, more frequent follow-up assessments, further diagnostic investigation, etc.)

This applies to any protocol and non-protocol specified safety and efficacy laboratory result from tests performed after the first dose of study medication that falls outside the laboratory reference range and meets the clinical significance criteria.

This does not apply to any abnormal laboratory result that falls outside the laboratory reference range but that does not meet the clinical significance criteria (these will be analyzed and reported as laboratory abnormalities), those that are considered AEs of the type explicitly exempted by the protocol, or those which are a result of an AE that has already been reported.

For purposes of this study, laboratory tests showing a decreased level of hFVIII activity should not be reported as adverse events unless signs of worsening are observed.

